Specific Aim 1: To determine the prevalence of *APOL1* renal risk variants among 2,600 HIV-positive individuals in Nigeria and assess whether *APOL1* HR status correlates with prevalent albuminuria, eGFR, and/or prevalent CKD (defined as macroalbuminuria or eGFR <60 ml/min/1.73 m²) in this population.

Hypothesis: ~25% of those screened will carry the *APOL1* HR genotype, which will be associated with albuminuria, lower baseline eGFR, higher uACR, and higher rates of prevalent CKD.

Definitions: Microalbuminuria will be defined as having a mean uACR of 30-300 mg/g. CKD will be defined by the presence of proteinuria or an eGFR of < 60 ml/min/1.73m².

Study Population: We will determine the prevalence of *APOL1* risk variants in a large group of HIV-positive adults (n = 2,600) in Nigeria and correlate them with early markers of kidney disease; namely microalbuminuria, reduced eGFR, and CKD. All consecutively seen HIV-positive ART-experienced (6+ months) adults (\geq 18-70 years of age) presenting for care at AKTH will be approached for enrolment into this study. **NOTE**: We will be enrolling ART-experienced adults (on ART for 6+ months). Specifically, if on ART for 6-12 months, then subjects need to have a plasma viral load value < 20 copies/mL from their 6-month blood draw, and if on ART for > 12 months, then enrolled participants need to have a suppressed viral load result (i.e. < 20 copies/mL) on their most recent viral load blood draw---which needs to be within the past 6 months). Routine viral load monitoring has only recently been implemented at our study site in north-central Nigeria, and by enrolling only patients with recent evidence of viral suppression, we will do our best to eliminate ongoing HIV-associated viral replication in non-adherent persons as a potential contributing cause to immune activation and therefore NCD end-organ complications, including kidney disease.

1.2 Specific Aim 2

Specific Aim 2: To assess whether RAAS inhibition with an ACEi compared to placebo, significantly reduces incidence of albuminuria or reduced eGFR among 280 HIV-positive individuals with microalbuminuria who are receiving ART.

Hypothesis: After two years,

- A significantly higher proportion of participants in the intervention vs. SOC arm will regress from microalbuminuria to normoalbuminuria (uACR<30 mg/g); anticipated hazard ratio = 2.5.

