- Significantly higher proportions of participants in the SOC arm (60% vs. 25% in the intervention arm) will progress from microalbuminuria to macroalbuminuria (uACR>300 mg/g).
- Albuminuria will fall by an average of 40% in the intervention arm and increase by an average of 10% in the SOC arm.

Study population: All HIV-positive ART-experienced (6+ months) screened individuals (n = 2,600) found to have i) confirmed microalbuminuria (mean uACR between 30-300 mg/d obtained at 2 separate measurements at least 4 and no more than 8 weeks apart), (NOTE: based on variability of individual uACR measurements, we also plan to call back Aim 1 participants having normoalbuminuria (especially those with an average uACR value in the 20-29 mg/g range) as well as Aim 1 participants having macroalbuminuria), and ii) fairly well-preserved renal function, namely an eGFR > 60 ml/min/1.73m²; will be approached for enrollment into this study. Based on recent studies at AKTH among HIV positive adults, we anticipate that a minimum of 18% of screened patients (n~460) will be eligible. Therefore, with a target sample size equal to

280 (see Section 10.0), 59% of eligible patients would need to consent for this Aim 2 study.

Primary Endpoints:

- i) Regression from microalbuminuria (uACR=30-300 mg/g) to normoalbuminuria (uACR < 30 mg/g)
- ii) Progression from microalbuminuria (uACR=30-300 mg/g) to macroalbuminuria (uACR > 300 mg/g) by study arm
- iii) Mean change in uACR

Secondary Endpoints:

i) Doubling of serum creatinine from baseline; ii) All-cause mortality (**NOTE**: Planned follow-up is two years for all participants), iii) Proportion experiencing a 40% decline in eGFR (using CKD-EPI-Cr-CyC equation), iv) Mean change in eGFR over time (using CKD-EPI-Cr-CyC equation), and v) change in clinical/performance status (as ascertained via two measures, specifically the WHO quality of life (WHOQOL-HIV) tool (31 questions)^{107,108} and the Karnofsky performance score)¹⁰⁹.

1.3 Specific Aim 3

Specific Aim 3: To determine whether the *APOL1* HR genotype is associated with worse longitudinal kidney outcomes among HIV-positive Nigerians with prevalent albuminuria, with regard to progression of albuminuria and eGFR decline.

Hypothesis: After two years of follow-up, independent of baseline uACR, eGFR, and/or treatment assignment:

- Study participants with the HR genotype will have a more rapid kidney function decline (median eGFR change) compared to those with the LR genotype.

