CA) targeting the 3 chromosome 22 APOL1 variants (rs73885319 [G1], rs60910145 [G1], and rs 71785313 [G2]) associated with CKD and HIV-associated kidney disease. The APOL1 risk alleles are defined by the G1 haplotypes (rs73885319-G/rs60910145-G and rs73885319-G/rs60910145-T) and by the G2 haplotype (rs71785313-deletion). We will infer the APOL1 genotype from the number of risk alleles: individuals exhibiting two risk alleles (G1/G1, G1/G2, or G2/G2) will be assigned to the "high-risk (HR)" group, while individuals carrying no or one risk allele (G0/G0, G0/G1, and G0/G2) will be attributed to the "low-risk (LR)" group. We will also examine the risk allele groups in a categorical manner (0 vs. 1 vs. 2 alleles and 0 vs. 1 risk alleles) to determine whether presence of a single risk allele poses increased risk. We will then determine the overall prevalence of APOL1 risk alleles, including odds ratios for baseline CKD and albuminuria, and the standard error for beta comparing levels of microalbuminuria and eGFR stratified by genotype (including testing for association between the APOL1 genotype and longitudinal eGFR slope using linear regressions). In addition, we will perform crude and adjusted linear regression analyses (modified Poisson regression) to test for associations with mean uACR, eGFR, and CKD, adjusting for sex, blood pressure, and age. Based on previous genetic association work in HIVAN, we will test both additive and recessive genetic models to capture all potential risk alleles associated with microalbuminuria and CKD. Because of the strong associations reported for APOL1 with HIVAN (OR=29, U.S. and OR 89, South African, recessive model), our cohort exhibits substantial power to detect the effects of APOL1 in the recessive model. For APOL1, we anticipate that 12% of controls and 36% of cases will carry the APOL1 HR genotype; this is a strong epidemiological association, but modest on the scale of known effects of APOL1 risk alleles on kidney disease.

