Statistical analysis plan: Our first approach will be to perform an intent-to-treat analysis, but we will also perform an on-treatment analysis to compare these data and present all available findings. *Primary analysis*: We will test the hypotheses that regression and progression rates are different across arms using multivariable Cox regression models with the intervention variable (randomization to RAAS [yes/no]) as the primary predictor variable, adjusting for baseline (pre-randomization) covariates including baseline uACR, *APOL1* renal risk variants, CD4+ cell count, blood pressure

ART regimen (DTG vs. other), and the presence/absence of comorbid medical conditions (hypertension, cardiovascular disease). To relax linearity assumptions, baseline uACR will be included in models using restricted cubic splines.¹³⁸ Primary analyses will be intention to treat, although we also plan to perform "per protocol" analysis. We will also test the impact of study arm on uACR using a linear mixed effects model to account for within patient correlation with the outcome of 3-monthly uACR values (with primary endpoints obtained by evaluating the uACR and other key renal outcomes at 18 and 30 months given that all enrolled study participants will not be placed or sustained on their maximum tolerated lisinopril dose or matched placebo until 6 months after study enrollment). The model will also adjust for the baseline covariates given above. For this analysis, we anticipate log-transforming uACR to meet modelling assumptions, although other transformations will be considered if needed.

Secondary analyses: Analyses for secondary endpoints will be similar to that described above. Time-to-event outcomes (doubling of serum creatinine from baseline, all-cause mortality, 40% decline in eGFR, and tenofovir toxicity) will be assessed using multivariable Cox regression models. Continuous outcomes (eGFR, quality of life metrics, and blood pressure) will be analyzed using mixed effects models after proper transformation of the outcome variable, if necessary. Baseline covariates listed above will be included in all secondary analyses.

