Statistical analysis and considerations: Analyses for Aim 3 will be the same as those outlined in Aim 2, except the predictor of interest will be APOL1 haplotype (high risk vs. low risk) instead of intervention arm; analyses will adjust for intervention arm (similar to how analyses of Aim 1 adjusted for APOL1 genotype). Assuming that ~30% (n = 84) of Aim 2 study participants have the high risk genotype, namely 2 copies of the risk variants (G1/G1, G1/G2, or G2/G2), with the remainder of Aim 2 study participants (n =196) having the low risk genotype (carrying no or one risk allele [G0/G0, G0/G1, and G0/G2]), and that the rate of progression will be similar to that hypothesized in Aim 2, we anticipate having 80% power to detect hazard ratios on the order of 2.4 to 3.2. Specifically, if the rate of regression is 22% (e.g., 10% and 25% in the SOC and intervention arms, respectively), we will have 80% power to detect a hazard ratio of 3.2 between the low and high risk genotypes; if the rate of regression is 35% (e.g., 20% and 40% in the SOC and intervention arms, respectively), we will have 80% power to detect a hazard ratio of 2.4. With regards to progression, if the overall event rate is 42.5%, we anticipate having 80% power to detect a hazard ratio of 2.1 between the high and low risk genotypes; if the overall rate of progression is 28%, we anticipate approximately 80% power to detect a hazard ratio of 2.5. Analyses will be repeated treating number of risk alleles (0, 1, or 2) as a categorical variable to investigate differences in risks when having 0 vs. 1 risk allele.

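### Aim 3 asks whether APOL1 high-risk carriers lose eGFR faster, but the analysis it inherits from Aim 2 states no genotype-by-time contrast and does not list baseline eGFR as a covariate

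*Combined protocol and SAP*

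**What the plan says.** The Aim 3 hypothesis (section 1.3) concerns a rate. It opens "After two years of follow-up, independent of baseline uACR, eGFR, and/or treatment assignment" and states that high-risk participants "will have a more rapid kidney function decline (median eGFR change) compared to those with the LR genotype".

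The analysis is in section 8.0, Specific Aim 3: "Analyses for Aim 3 will be the same as those outlined in Aim 2, except the predictor of interest will be APOL1 haplotype", with adjustment for intervention arm. The Aim 2 text it points to says "Continuous outcomes (eGFR, quality of life metrics, and blood pressure) will be analyzed using mixed effects models", by analogy with the uACR model, whose outcome is the 3-monthly values. Covariate adjustment is described as "adjusting for baseline (pre-randomization) covariates including baseline uACR", followed by APOL1, CD4+ count, blood pressure, ART regimen and comorbidities. Baseline eGFR is not on that list. No time term, predictor-by-time term or random slope is written.

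Three other places bear on the point:

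- The Aim 1 hypothesis (section 1.1) expects the high-risk genotype, "which will be associated with albuminuria, lower baseline eGFR, higher uACR, and higher rates of prevalent CKD".
- The Aim 2 secondary endpoint is worded "Mean change in eGFR over time (using CKD-EPI-Cr-CyC equation".
- The genetics paragraph of section 5.0, under the Aim 1 procedures, mentions "testing for association between the APOL1 genotype and longitudinal eGFR slope using linear regressions". Section 8.0 does not carry this into Aim 3.

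**The concern.** In a randomised comparison the arms start equal in expectation, so a difference in average eGFR during follow-up can stand for a difference in change. That logic fails when genotype replaces arm. The stratified randomisation balances arms within genotype. It does nothing to equalise eGFR between genotypes, and neither does the entry floor of 60 mL/min/1.73m².

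Two errors follow if the inherited model is fitted literally. Parallel trajectories with a lower high-risk starting point would be read as faster decline. And a real difference in slope would be diluted, because it is averaged over visits and set against the large between-person spread in eGFR level. The kidney-function half of Aim 3 rests on this result.

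The hypothesis also names a median change, and no planned model estimates a median.

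**Working it through.** **The plan's own figure.** Table S5 gives the only power figure for continuous eGFR, by arm. With 126 per arm and two-sided 5% (assumed; the table does not state alpha):

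- 80% power: (1.960 + 0.842) × √(2/126) = 0.353 SD
- 90% power: (1.960 + 1.282) × √(2/126) = 0.408 SD

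This reproduces the stated 0.35 and 0.41. There is no corresponding figure by genotype. On the 84:196 split, 80% power needs 2.802 × √(1/84 + 1/196) = 0.37 SD. After 10% loss (about 76 and 176) it needs 2.802 × √(1/76 + 1/176) = 0.38 SD.

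**Inputs for the comparison of models.** From the documents: the 84:196 split, 10% loss, and visits at months 0, 3, …, 24 (nine values). Assumed, because the documents give none: between-person SD σ₀ = 15–20, slope SD σ₁ = 3–5 per year, residual SD σₑ = 6–8 mL/min/1.73m², no intercept–slope correlation. The baseline gap d₀ and slope difference d₁ are also assumed.

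**Formulas.** Time is in years, with mean 1 and sum of squares about the mean 3.75. Let k = 1/76 + 1/176 = 0.01884. The rejection rate is Φ(|effect|/SE − 1.96) + Φ(−|effect|/SE − 1.96).

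- Level (genotype main effect, random intercept): effect d₀ + d₁; SE² = k(σ₀² + σ₁² + σₑ²/9).
- Level adjusted for measured baseline eGFR (mean of the eight later visits): b = σ₀²/(σ₀² + σₑ²); effect (1 − b)d₀ + 1.125d₁; SE² = k(σ₀² + 1.125²σ₁² + σₑ²/8 − bσ₀²).
- Genotype-by-time: effect d₁; SE² = k(σ₁² + σₑ²/3.75).

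**Worked case, σ₀ = 20, σ₁ = 5, σₑ = 8.**

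- Level: SE = √(0.01884 × 432.1) = 2.85. Gap of 5, equal slopes: 5/2.85 = 1.75, rejected 42% of the time. Slope difference of 2, equal start: 2/2.85 = 0.70, power 11%.
- Baseline-adjusted: b = 400/464 = 0.862; SE = √(0.01884 × 94.8) = 1.34. A gap of 5 leaves 0.138 × 5 = 0.69, rejected 8%. Slope difference of 2: 2.25/1.34 = 1.68, power 39%.
- Genotype-by-time: SE = √(0.01884 × 42.07) = 0.89. Gap of 5: 5%. Slope difference of 2: 2/0.89 = 2.25, power 61%.

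**Range over all eight SD combinations:**

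| Truth (mL/min/1.73m²) | Level | Level + baseline eGFR | Genotype × time |
|---|---|---|---|
| Gap 3, equal slopes | 18–29% | 6–9% | 5% |
| Gap 5, equal slopes | 42–66% | 7–16% | 5% |
| Gap 8, equal slopes | 80–97% | 9–34% | 5% |
| Slope difference 2/year, equal start | 11–16% | 39–67% | 61–92% |
| Slope difference 3/year, equal start | 18–29% | 71–95% | 92% to over 99% |

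Adding a random slope without the interaction does not help: power for differences of 2–3 per year is then 5–15%.

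**Cross-check.** A simulation used the full 84:196, visits at months 3–24, between-person SD 18, slope SD 2.5, within-person SD 5–8 and entry on two eGFR values of at least 60. With gaps of 3, 5 and 8 and equal slopes, the level model rejected in about 20%, 45% and 80–84% of trials, the baseline-adjusted model in 6–19%, and genotype-by-time in about 5%. For a 2 per year slope difference, power was 17–19%, 55–85% and 78–98% respectively.

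**The case against.** The strongest reply is that the plan is brief here and not wrong. Section 8.0 is a summary and not a model formula. The inherited endpoint is worded as change over time, and Table S5 is labelled the same way. The Aim 3 hypothesis says independent of baseline eGFR, and the covariate list is introduced by a word that leaves it open. Section 5.0 mentions a genotype test on eGFR slope; since Aim 1 takes one blood sample for eGFR, that sentence most naturally refers to follow-up data. The Cox analysis of a 40% eGFR decline also carries over to genotype, and a parallel lower trajectory does not by itself meet a relative threshold. Finally, the expected baseline gap is a hypothesis about the 2,600 screened, with no size given, and the Aim 2 entry limits may narrow it.

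Much of this stands. A reader might infer that the plan commits to a model of eGFR level and that a real difference in decline would mostly be missed. The documents do not support that: the time structure is unspecified, and the low power applies only to the unadjusted level reading.

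The reply does not close the gap, for four reasons.

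- The change label does not settle the model. The uACR endpoint is also called mean change, yet Table S1 powers it as a comparison of means after follow-up.
- Evaluating outcomes at named months, as section 8.0 proposes, gives a level at that visit unless baseline is handled. In the worked case at month 24, SE = √(0.01884 × (400 + 4 × 25 + 64)) = 3.26, and a gap of 5 alone is rejected about 34% of the time.
- The slope sentence sits under Aim 1, without detail, and the Aim 3 text does not refer to it.
- The 40% threshold shows who crosses a line. It does not estimate a rate.

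**Conclusion.** The concern holds in a conditional form. The Aim 3 eGFR hypothesis is about rate of decline independent of baseline eGFR, while the analysis as written names neither a genotype-by-time contrast nor baseline eGFR adjustment. A literal fit could report a starting difference as faster decline and would have little power for a true slope difference.

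The direction follows from the text. The size does not: every SD, gap and slope difference above is assumed. It also depends on how the analyst fills the silence. Adjusting for baseline eGFR removes most of the false signal but not all, because one measured baseline is noisy, and it leaves power below that of the slope contrast in these settings. This is a should-fix clarification of the estimand for a stated hypothesis, and it does not undermine the randomised comparison in Aim 2.

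**What to change.** In section 8.0, Specific Aim 3, give eGFR its own sentence: a linear mixed model of 3-monthly eGFR with random intercept and random slope, and fixed effects for genotype, time, genotype-by-time, arm, arm-by-time and the listed covariates. The Aim 3 eGFR result is the genotype-by-time coefficient, in mL/min/1.73m² per year, with its 95% CI. Give change from baseline adjusted for baseline eGFR as a supporting analysis.

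Reconcile the other places: replace the median change in section 1.3 with the mean slope difference, move the slope test in section 5.0 from Aim 1 to Aim 3, and align the Aim 2 model description in section 8.0.

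The cost is SAP wording and two interaction terms, with no new data, visits or participants. The downside is the linear-slope assumption, which may fit poorly around dose titration and the creatinine step that the plan expects after a switch to dolutegravir. Check it with a flexible time term and with the time-varying dolutegravir covariate already planned as a sensitivity analysis.

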- Study participants with the LR genotype will have 30% lower mean uACR values (compared to baseline) compared to study participants with the HR genotype.

Study population: All enrolled Aim 2 study participants who completed the study, namely, two years of study follow-up. However, to improve our power to evaluate the influence of *APOL1* risk allele status on key renal outcomes, we will include all enrolled Aim 2 study participants that completed a minimum of one year of clinical follow-up, meaning that if they were lost to follow-up after completing their one-year study visit, we will include them in our Aim 3 genetics outcome analyses.

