enroll 280 eligible patients from Specific Aim 1 for 1:1 randomization in our RCT for Specific Aim 2. Based on our prior experience with ongoing RCTs in the study location, we anticipate that enrollment into Aim 2 will take 12 months and there will be 10% loss to follow up at end of year 2, yielding 252 patients on study (126 per arm). Aim 2A: At 2 years, we hypothesize that a higher proportion of intervention participants will regress from microalbuminuria to normoalbuminuria (uACR < 30 mg/g) with a hazard ratio (HR)= 2.50. Using the logrank test, we will have approximately 80% power if the rate of regression in the SOC arm is at least 12%, and 90% power if that rate is 16% or higher with a 1.7% type I error¹³⁶. (The type I error rate was set at 5%/3=1.7% to account for multiple testing and the fact that we have 3 primary endpoints.) See Tables 3 and 4. Aim 2B: At 2 years, we hypothesize that a higher proportion of patients in the SOC arm. namely 60% vs. 25% in the intervention arm (HR≈0.42), will progress from microalbuminuria to macroalbuminuria (uACR > 300 mg/g). With 126 patients per arm (after removing 10% loss to follow-up), we will have >95% power for Aim 2B with a 1.7% type I error. See Tables 5 and 6. Figure 3 shows changes in Aim 2A power for varying SOC regression rates and changes in Aim 2B power for varying sample size. The sample size for Aim 2C is such that we will have approximately 80% power to detect at the alpha=0.017 level a difference in the log-transformed mean uACR of 0.24, which is approximately 0.41 standard deviations. These power calculations are likely conservative, as they do not incorporate baseline covariates, which will be included in the actual analyses (see below) and should improve power; in addition, the uACR analysis will incorporate multiple longitudinal measures per person whereas these power calculations only assume a single final measurement per person.

The sample size was chosen to have sufficient power for all primary endpoints. Tables S1-S8, investigating power and detectable alternatives for the secondary endpoints with a total sample size of 280 are provided in Appendix B. In short, we anticipate low power to detect differences between intervention arms in the doubling of serum creatinine, all-

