Appendix B. Supplemental tables - Statistical calculations for secondary endpoints

Table S1. Detectable differences in means of log-transformed uACR values. The outcome is uACR measurement (units= mg/g) and a t-test will be used to compare the two means of log-transformed uACR for the two arms after follow-up. Given the inclusion criteria with the uACR range of 30-300 mg/g, we assume the log-transformed uACR has

a 95% probability interval from 3.4 to 5.7 and a standard deviation of 0.58. With 90 subjects at the end of study after adjustment for 10% loss to follow up (LTFU), we will have 80% power to detect a difference of 0.42 units of standard deviation (0.24 on log-transformed means assuming standard deviation of 0.58).

,		
alpha	Subjects per	Detectable
	Arm	Difference
0.010	100	0.30
0.010	120	0.27
0.010	140	0.25
0.010	160	0.23
0.010	180	0.22
0.017	100	0.28
0.017	120	0.25
0.017	140	0.24
0.017	160	0.22
0.017	180	0.21
0.025	100	0.27
0.025	120	0.24
0.025	140	0.23
0.025	160	0.21
0.025	180	0.20
0.050	100	0.24
0.050	120	0.22
0.050	140	0.20
0.050	160	0.19
0.050	180	0.18

Table S2. Detectable differences in doubling of serum creatinine. Assuming 2% - 20% of subjects in the SOC arm will be doubling of serum creatinine, we will use an uncorrected chi-squared test to detect the difference between the two arms. In case of 10% of subjects on the SOC arm will have their serum creatinine doubled after follow up, we will have 80% power to detect a 9.3% decrease on the experimental arm to 0.7% (RR=0.07).

Alpha	Rate SOC	Detectable	Rate Exp
	arm	RR	arm
0.01	0.10	0.050	0.005
0.01	0.15	0.193	0.029
0.01	0.20	0.290	0.058
0.05	0.10	0.180	0.018
0.05	0.15	0.307	0.046
0.05	0.20	0.395	0.079

Table S3. All-cause mortality. With 140 patients on each arm, we will have 126 patients on each arm at the end of study assuming 10% LTFU. An uncorrected chi-square test will be used to test the difference of the all-cause mortality between the two arms. In case of the all-cause mortality is 10% on the SOC arm, we will have 80% power to detect an absolute 8.2% decrease on the treatment arm to 1.8%.

Rate of SOC	Power	Detectable Difference	RR	Detectable Rate Exp Arm
0.08	0.8	0.072	0.10	0.008
0.08	0.9	0.079	0.01	0.001
0.10	0.8	0.082	0.18	0.018
0.10	0.9	0.091	0.09	0.009
0.12	0.8	0.092	0.23	0.028
0.12	0.9	0.102	0.15	0.018
0.14	0.8	0.100	0.29	0.040
0.14	0.9	0.112	0.20	0.028
0.16	0.8	0.108	0.32	0.052
0.16	0.9	0.121	0.24	0.039
0.18	0.8	0.115	0.36	0.065
0.18	0.9	0.129	0.28	0.051

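### Aim 3 drops participants with under one year of follow-up although its models can use them, and the inputs and hazard ratios in its power paragraph do not agree

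*Combined protocol and SAP*

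**What the plan says.** **Analysis set.** Section 1.3 first defines the Aim 3 population as "All enrolled Aim 2 study participants who completed the study, namely, two years of study follow-up". To gain power it then relaxes this: "we will include all enrolled Aim 2 study participants that completed a minimum of one year of clinical follow-up". People lost after the one-year visit are kept; people lost before it are not.

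**Models.** Section 8.0, Specific Aim 3, states "Analyses for Aim 3 will be the same as those outlined in Aim 2", with genotype replacing treatment arm as the predictor. The Aim 2 analyses are Cox models for regression and progression and a linear mixed model on three-monthly uACR, primarily by intention to treat.

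**Power.** The same Aim 3 paragraph begins "Assuming that ~30% (n = 84) of Aim 2 study participants have the high risk genotype" and gives the other 196 as low risk, 280 in total. It claims 80% power for four hazard ratios:
- Regression, HR 3.2: "if the rate of regression is 22% (e.g., 10% and 25% in the SOC and intervention arms, respectively").
- Regression, HR 2.4: "if the rate of regression is 35% (e.g., 20% and 40% in the SOC and intervention arms, respectively").
- Progression, HR 2.1 at an overall rate of 42.5%.
- Progression, HR 2.5 at an overall rate of 28%.

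No alpha is given for Aim 3. For Aim 2, Section 8.0 plans that "there will be 10% loss to follow up at end of year 2, yielding 252 patients on study (126 per arm") and uses alpha 0.017.

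**The concern.** Requiring a year of follow-up conditions the analysis on something that happens after baseline. A participant who progresses at month 6 and is lost at month 9 contributes nothing, although a Cox model would count the event and a mixed model would use the visits. If leaving early is related to both genotype and outcome, the genotype effect is distorted.

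The selection is direct for all-cause mortality, if Aim 3 inherits that endpoint through the reuse of the Aim 2 analyses. For renal endpoints it is only potential. Section 7.0 lists a serious adverse event among circumstances requiring discontinuation, and the dose titration table in Section 6.0 makes a 30–50% eGFR decline an SAE, so a kidney outcome could itself lead to exclusion.

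The power paragraph counts all 280, with neither the one-year rule nor the 10% loss. Its event rates, high-risk share and hazard ratios also conflict with each other or with the rest of the plan. A reader cannot tell what Aim 3 was planned on.

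**Working it through.** **1. Formula, checked on the plan's own tables.** With D events, a share p in one group and two-sided alpha,

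power = Φ(√(D·p(1−p))·|ln HR| − z₁₋α/₂), and detectable HR = exp[(z₁₋α/₂ + z₀.₈)/√(D·p(1−p))].

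With p = 0.5 and alpha 0.017, this reproduces the Aim 2 power tables in Section 8.0:
- Regression, HR 2.5: 53 events give 0.829 (stated 0.828); 71 events give 0.930 (stated 0.928).
- Progression, HR 0.42: 107 events give 0.982 (stated 0.984).

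**2. Event rates.** Under 1:1 randomisation (10% + 25%)/2 = 17.5%, not 22%, and (20% + 40%)/2 = 30%, not 35%. By contrast 42.5% is exactly (60% + 25%)/2, the Aim 2 progression rates, so simple averaging is evidently the intended method.

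**3. Stated inputs.** Take N = 280, p = 0.30 and the stated rates. For the first regression case D = 280 × 0.22 = 61.6 and √(61.6 × 0.21) = 3.597. At alpha 0.017 the detectable HR is exp[(2.387 + 0.842)/3.597] = 2.45. All four, in the paragraph's order:

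| Inputs | Regression 1 | Regression 2 | Progression 1 | Progression 2 |
|---|---|---|---|---|
| Stated in Section 8.0 | 3.2 | 2.4 | 2.1 | 2.5 |
| N=280, 30%, stated rates, alpha 0.017 | 2.45 | 2.04 | 1.91 | 2.22 |
| N=280, 30%, stated rates, alpha 0.05 | 2.18 | 1.85 | 1.75 | 1.99 |
| N=180, 25%, rates 17.5/30/42.5/28%, alpha 0.05 | 3.17 | 2.41 | 2.10 | 2.49 |
| N=252, 25%, same corrected rates, alpha 0.017 | 3.07 | 2.36 | 2.06 | 2.43 |
| N=252, 25%, same corrected rates, alpha 0.05 | 2.65 | 2.10 | 1.87 | 2.16 |

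On the stated inputs, power at the stated hazard ratios is 91–96% (alpha 0.017) or 96–99% (alpha 0.05), not 80%. Freedman's formula with unequal allocation and a two-proportion test also fail to give 80% within two points for all four.

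**4. Where the figures may come from.** I scanned N from 150 to 299, with 25% or 30% high risk and alpha 0.05, 0.017 or 0.01. No combination using 22% and 35% matches all four stated values to one decimal. With 17.5% and 30% there are 58 matches, including N = 174–181 (25%, alpha 0.05) and N = 231–241 (25%, alpha 0.017). N = 180 has some support: the Table S1 text in Appendix B still reads "With 90 subjects at the end of study after adjustment for 10% loss to follow up (LTFU"), and 2 × 90 = 180. A t-test with 90 per arm at alpha 0.05 detects 0.42 SD at 80% power, as that text states.

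**5. High-risk share.** The two-risk-allele strata in Section 5.0 hold about 35 + 35 = 70 of 280, which is 25%. The power paragraph uses 84, which is 30%.

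**6. Size of the selection.** Ten per cent two-year loss is 28 of 280; if loss is even over time, about 14 leave before month 12. I simulated 4,000,000 participants per setting with exponential times, 25% high risk, low-risk 24-month progression 36% and true HR 2.1 (about 115 events per 280). Background loss was 6%, or 10% in the first setting. Year-1 progressors who leave do so after the event and before month 12. Among those with at least 12 months of follow-up:

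| Who leaves | HR | Events lost | Two-year loss |
|---|---|---|---|
| 10%, unrelated to outcome | 2.10 | 1.6% | 10% |
| 10% of year-1 progressors, both genotypes | 2.10 | 6.7% | 8.3% |
| 20% of high-risk, 10% of low-risk year-1 progressors | 1.99 | 8.9% (about 10 of 115) | 9.2% |

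For mortality, a constant hazard at 10% over two years puts (1 − √0.9)/0.1 = 51% of deaths before month 12, all of which would be dropped.

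**The case against.** **Consequences are small.** This is largely right. With N = 252, 25%, alpha 0.017 and corrected rates, power at the stated hazard ratios is 82–83%, so the 80% claim is about right for the design as described elsewhere. Sample size rests on Aim 2. Two of the three simulations show no bias, and nothing in the documents supports high-risk progressors leaving twice as often.

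**Thirty per cent may reflect enrichment.** Section 1.1 expects the high-risk genotype to be associated with albuminuria, and Section 5.0 anticipates 36% among cases. The detectable relative risk of 1.37 in Section 8.0 would give 0.25 × 1.37/(0.25 × 1.37 + 0.75) = 31% among microalbuminuric participants. So 30% is plausible, but the plan does not give this as the reason, and 84 against 70 still needs reconciling. At 30%, N = 252 and alpha 0.017 the detectable values are 2.89, 2.25, 1.98 and 2.31.

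**The smaller-design explanation is conjecture.** It is an inference, with many other matches. The mismatch does not depend on it.

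**The routes to selection are uncertain.** Section 1.3 frames Aim 3 around albuminuria and eGFR; mortality enters only through the reuse of the Aim 2 analyses, and Section 8.0 expects it below 10%. Section 6.0 handles eGFR falls by holding and rechecking, which sits awkwardly with Section 7.0; those sections must be reconciled. The simulation models albuminuria progressors leaving, not the eGFR route.

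**The 84 and 196 may only describe genotype shares.** Even so, the plan gives no N for the set it says it will analyse.

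**Conclusion.** Both parts hold. The one-year rule discards usable data and adds a post-baseline selection that the planned models do not need. Its likely effect is modest: no bias when leaving is unrelated to genotype, and a fall from 2.10 to 1.99 under an assumed two-fold difference in leaving among progressors. The power paragraph is wrong as written: two event rates contradict their own arm rates, and the four hazard ratios do not follow from the stated N, share and rates at alpha 0.05 or 0.017.

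The power error understates power, so Aim 3 is not shown to be underpowered. The recalculation rests on the event-based formula in step 1 and on an assumed alpha, since none is stated. This should be corrected before analysis, but it does not threaten the trial.

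**What to change.** - **Analysis set:** define it once, identically in Sections 1.3 and 8.0, as all randomised Aim 2 participants with a genotype, censored at last visit in Cox models and with all available visits in mixed models. Keep the one-year set as a sensitivity analysis. State that the analysis still assumes non-informative dropout.
- **Endpoints:** say whether Aim 3 includes all-cause mortality.
- **Power paragraph:** use 17.5% and 30% for regression, one N, a high-risk share reconciled with the Section 5.0 strata (with the reason if it stays at 30%), and a stated alpha. For example, N = 252, 25% and alpha 0.017 give 3.07, 2.36, 2.06 and 2.43. Correct the summary range of 2.4 to 3.2, which omits the paragraph's own 2.1.
- **Appendix B:** update the Table S1 text from 90 subjects to the current N.

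The cost is SAP wording and one recalculated paragraph, with no new data and no extra patients.
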